9.0 TOXICITIES AND DOSING MODIFICATIONS

9.1 Assessment of adverse events

The patient's pre-existing conditions will be recorded, including signs and symptoms of the disease. Subjects will be monitored for AEs from the time of informed consent through their last follow-up visit (30 days after the date of the last dose of cabozantinib or pembrolizumab treatment, whichever occurs last). Subjects will be instructed to notify the investigator immediately at the onset of any AE experienced. Moreover, AEs will be assessed at scheduled study visits or non-study clinic visits. In addition, any SAE attributed to treatment occurring after the last follow-up visit will also be recorded.

All AEs and changes in pre-existing conditions will be documented, whether related or unrelated to study treatment. Seriousness, severity grade, and relationship to study treatment or protocol procedure will be determined by the investigator and reported on the CRF. The NCI CTCAE v5 will be used to grade AEs. For AEs not listed in the CTCAE v5, the investigator will be responsible for selecting the appropriate system organ and severity grade based on their clinical judgement. SAEs that occur after signing the consent form but prior to receiving study treatment will not be reported as serious unless the event was caused by a protocol procedure.

See Section 16.0 for definitions and guidelines on monitoring and reporting of AEs and SAEs.

9.2 General guidelines about toxicity assessment and management in combination therapy

Both non-immune and immune-related toxicities may occur on study. Any AE that occurs on study will be assessed for grade and attribution to either cabozantinib, pembrolizumab, or both agents.

RG1007034

Cabozantinib and pembrolizumab have class-specific safety profiles based on their mechanisms of action but may also cause overlapping AEs. Examples of VEGFR TKI-associated AEs caused by cabozantinib are hypertension and hand-foot syndrome. Examples of immune-related AEs caused by pembrolizumab are pneumonitis and endocrinopathies. Examples of overlapping AEs are diarrhea and ALT or AST elevations. To distinguish the toxicities of these two agents, the known toxicity profiles and typical timeline of toxicities associated with both study drugs should be taken into account.⁵⁷ For instance, in the CELESTIAL trial, the median onset of diarrhea among patients who received cabozantinib was 4.1 weeks.²¹ Immune-related AEs may occur shortly after the first dose or several months after the last dose of pembrolizumab treatment, and may affect more than one organ system simultaneously.

Therefore, if an AE is believed to be possibly related to or exacerbated by cabozantinib only, then it must be managed accordingly and cabozantinib may need to be interrupted and/or dose-adjusted. In this setting, pembrolizumab may be continued if the patient can tolerate it as per discretion of the investigator. However, it is recommended to hold pembrolizumab as well in the setting of severe (grade 3 or higher) AEs related to cabozantinib alone.

In contrast, if an AE is believed to be possibly related to or exacerbated by pembrolizumab, then both agents should be interrupted according to the guidelines below, even if the AE is not attributed to cabozantinib.

For immune-related AEs (irAEs), early recognition and initiation of treatment is critical to reduce complications. Based on existing clinical study data, most irAEs were reversible and could be managed with interruptions of pembrolizumab, administration of corticosteroids and/or other supportive care. For suspected irAEs, ensure adequate evaluation to confirm etiology or exclude other causes. Additional procedures or tests such as bronchoscopy, endoscopy, skin biopsy may be included as part of the evaluation. Based on the severity of irAEs, pembrolizumab may be held or permanently discontinued and steroids may be administered.

Guidance on dose modification of cabozantinib and pembrolizumab in the setting of specific AEs is provided in Sections 9.3 and 9.5, but management may differ from this guidance based on the clinical judgement of the investigator.

If one agent needs to be discontinued indefinitely due to toxicity, the other agent may be continued if the patient can tolerate it as per discretion of the investigator.

All dose interruptions and adjustments must be recorded clearly and accurately in the CRF, including dates of stopping and resuming drug(s), doses, and reasons for changes. In the event of a treatment pause, subsequent visits/cycles should not be delayed.

9.3 Information on cabozantinib toxicity

AEs may occur within the first few weeks after starting cabozantinib (steady state reached at approximately 2 weeks). Cabozantinib-related AEs that generally have an early onset include hypocalcemia, hypokalemia, thrombocytopenia, hypertension, PPES, abdominal pain, mucosal inflammation, constipation, diarrhea, and vomiting.

AEs should be managed with supportive care at the earliest signs of toxicity. In all subjects, dose delays and reductions of cabozantinib to manage toxicity are allowed under the guidelines below. In general, grade 3 cabozantinib-related AEs require dose interruption until AEs recover to grade 1, at which point treatment may be resumed at the next lower dose. Moreover, dose reductions are recommended for

grade 2 events that, if persistent, could become serious and/or intolerable. **If cabozantinib is delayed by more than 4 weeks, it must be discontinued**, unless there is reason to believe that the patient will benefit from resuming cabozantinib. In this case, resuming cabozantinib at dose reduction must be discussed with the PI.

Furthermore, cabozantinib should be discontinued for the following AEs: visceral perforation or fistula formation, severe hemorrhage, serious arterial thromboembolic events, nephrotic syndrome, hypertensive emergency, persistent uncontrolled hypertension despite optimal medical management, and RPLS.

If an AE is believed to be probably/definitely related to cabozantinib, and not related to pembrolizumab, then pembrolizumab may be continued even if cabozantinib needs to be interrupted or discontinued, as long as pembrolizumab is not expected to delay recovery or worsen the AE.

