AEs may occur within the first few weeks in the course of treatment with cabozantinib, as the drug is expected to reach steady state exposure at approximately 2 weeks following the first dose. Events that generally have an early onset include hypocalcemia, hypokalemia, thrombocytopenia, hypertension, PPES, abdominal pain, mucosal inflammation, constipation, diarrhea, and vomiting. AEs should be managed with supportive care at the earliest signs of toxicity. Dose reductions and treatment interruptions/delays should be considered. Dose reductions are recommended for events that, if persistent, could become serious or intolerable (see Section 9.0).

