9.4 Dose levels of cabozantinib

Cabozantinib must be started at 40 mg orally once daily and reduced to 20 mg orally once daily (minimum dose) for toxicity. Cabozantinib must be discontinued permanently if the minimal dose is not tolerated. Re-escalation to 40 mg once daily is not recommended, but may be allowed if there is a reason to believe that the patient will tolerate this dose after discussion with the PI.

Table 9.4.1. Dose levels for cabozantinib		
Dose Adjustment Level	Oral Dose	Frequency
0 (starting dose)	40 mg	Once daily
-1	20 mg	Once daily
-2		Discontinue

9.5 Guidance on dose modification of cabozantinib and pembrolizumab for non-immune and immune toxicities

Both non-immune and immune-mediated toxicities may occur on study.

The sections below provide guidance on dose modifications for TRAEs, in addition to management recommendations for cabozantinib-specific toxicities discussed in Section 9.3. However, management

RG1007034

may differ from this guidance based on the clinical judgement of the investigator. In all patients, supportive care should be initiated to manage the AEs in addition to dose modification of study drugs.

For potential irAEs, please refer to the ASCO Clinical Practice Guidelines for Management of Immune-Related Adverse Events in Patients Treated With Immune Checkpoint Inhibitor Therapy.⁵⁸

If dose is interrupted for TRAEs, cabozantinib must be resumed within 4 weeks of last dose, and pembrolizumab must be resumed within 12 weeks of last dose. Resuming drugs beyond these time points must be discussed with the Study PI.

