9.5.1 Non-immune toxicities

Table 9.5.1.1 below provides guidance for dose modification for non-immune toxicities in general. Pembrolizumab should be held if the AE is clinically severe and/or if pembrolizumab might delay recovery or worsen the AE.

Table 9.5.1.1. General guidance on dose modification for non-immune toxicities

Grade per CTCAE v5	Cabozantinib modification	Pembrolizumab modification
Hematologic TRAEs		
Grade 1 and 2	
No modification.	
No modification.
Grade 3 or 4 anemia, neutropenia, thrombocytopenia ¹	
Hold drug until recovery to grade 1, then restart at same dose level OR at reduced dose level (at the discretion of the investigator).1st and 2nd recurrence: hold drug until recovery to grade 1, then restart at reduced dose level (if not already reduced) or discontinue drug (if previously reduced dose).	
No modification.No modification. Consider holding drug if no improvement after holding cabozantinib.
Non-hematologic TRAEs		
Grade 1 or 2	
No modification (may be held for significantly symptomatic grade 2 toxicity). Supportive care as indicated.	
No modification.
Grade 3	
Hold drug until recovery to grade 1. If supportive care can be used and optimized to control symptoms, then restart at the same dose level. If grade 3 toxicity occurred on maximal supportive care then restart at reduced dose level.	
Hold drug until recovery to grade 1 (or pretreatment baseline), then restart drug.

	
 • 1st and 2nd recurrence despite optimal supportive care: hold drug until recovery to grade 1, then restart at reduced dose level (if not already reduced) or discontinue drug (if previously reduced dose). 	
Grade 4	
 • Hold drug and provide supportive care until recovery to grade 1, then restart at reduced dose level if the patient is deriving clinical benefit as determined by the treating investigator. • 1st recurrence: discontinued drug. 	
 • Hold drug until recovery to grade 1 (or pretreatment baseline), then restart drug.

TRAE, treatment-related adverse event.

¹Supportive transfusions and use of G-CSF recommended as per institutional guidelines.

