17.2 Statistical methods

The primary endpoint is ORR per RECIST v1.1, while secondary endpoints include ORR by iRECIST, ORR and DCR by iRECIST, median PFS, and median OS. Only patients who have been on treatment with both cabozantinib and pembrolizumab concurrently for more than 42 days in the first 3 cycles (i.e. received treatment for two-thirds of the cycle) will be included in the analysis of the primary endpoint. Patients who have received any duration of study treatment will be evaluable for safety.

Binary endpoints will be summarized by percentages and associated confidence intervals. ORR will also be represented by a waterfall plot. The distribution for survival times will be estimated using the method of Kaplan-Meier; associated landmark time percentages and the median value will be based on this. Confidence intervals for median values will use the Brookmeyer-Crowley method. Any toxicity with at least 5% prevalence has at least an 77% chance of being observed among 29 patients.

For the exploratory objectives, archival or fresh tumors from all patients will be analyzed by IHC, the presence of specific immune cell subsets and protein marker expression, as well as the staining pattern and location within tumors will be described. The frequencies of immune cell subset will be obtained from flow cytometry at various timepoints, and cell changes from baseline to post-treatment timepoints will be averaged across patients. The association between immune cell, biomarker expression, gene expression signature, or cytokine level with ORR will be evaluated using Spearman correlation, where $p<0.05$ is considered significant.

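### Section 17.2 limits the primary ORR to patients with more than 42 days on both drugs in the first 63, and plans no RECIST v1.1 ORR in all treated patients

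*Combined protocol and SAP*

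**What the plan says.** **Analysis sets (17.2).** The primary endpoint is analysed only in patients "on treatment with both cabozantinib and pembrolizumab concurrently for more than 42 days in the first 3 cycles", which a parenthesis explains as two-thirds. Safety uses a wider set: "Patients who have received any duration of study treatment will be evaluable for safety". No ORR by RECIST v1.1 is planned in that wider set.

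**Decision rule (17.1).** Thirteen patients enter stage 1 and the trial stops at 2 or fewer responses. Otherwise it continues to 29, and the 20% null is rejected at 9 or more responses. The stated type I error is 0.10, with 80% power at 38%. Enrolling beyond 29 is foreseen only for screen failures and for dropouts before treatment starts.

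**Holds (9.2, 9.5, 9.5.5).** After toxicity, cabozantinib may be held up to 4 weeks and pembrolizumab up to 12 weeks, or longer after discussion with the study PI. When pembrolizumab is held for an immune-related event, cabozantinib should be held as well. The calendar keeps running: "In the event of a treatment pause, subsequent visits/cycles should not be delayed".

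**Reductions (9.3).** Cabozantinib may also be reduced without a hold; this is the advice for "grade 2 events that, if persistent, could become serious and/or intolerable".

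**Imaging (11.2).** The first scheduled on-treatment scan falls at the end of cycle 3.

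**The concern.** In a single-arm trial judged on a response count, the denominator should be fixed by who started treatment. Here it is fixed by how the first nine weeks went.

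A patient who dies, progresses clinically or stops for toxicity within the first six weeks is treated, is counted for safety, and drops out of the ORR. Death or clinical progression in that period comes before the first scheduled scan, so these patients would almost always be non-responders. Removing them raises the reported rate.

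A long hold can work in either direction. A patient held for three weeks may still show a response on the cycle 3 scan and yet be left out.

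The reader of the final report would have no all-treated RECIST v1.1 figure from which to judge how far the filter moved the result.

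**Working it through.** **1. The plan's own figure.** Inputs from 17.1: n1 = 13, continue at 3 or more responses, n = 29, reject at 9 or more. With X1 ~ Bin(13, p) and X2 ~ Bin(16, p),

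P(reject) = Σ over x = 3…13 of P(X1 = x) · P(X2 ≥ 9 − x).

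This gives 0.0999 at p = 0.20 and 0.8044 at p = 0.38. The stated 0.10 and 80% reproduce.

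**2. Day count.** Assumption: held days do not count as days on both drugs. The window is 3 × 21 = 63 days and is not extended by a pause.

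| Days held | Days left | More than 42? |
|---|---|---|
| 20 | 63 − 20 = 43 | yes, included |
| 21 | 63 − 21 = 42 | no, excluded |
| 28 | 63 − 28 = 35 | no, excluded |

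A hold of 21 to 28 days is therefore within the cabozantinib limit but removes the patient. At exactly 21 days the two parts of 17.2 differ: 42/63 is two-thirds, but it is not more than 42 days.

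**3. Effect at the cut-off.** Intervals are Clopper-Pearson 95%.

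| Case | Reported ORR | Result |
|---|---|---|
| No exclusion | 9/29 = 31.0% (15.3–50.8) | rejects |
| Two non-responders excluded | 9/27 = 33.3% (16.5–54.0) | 9 responses, unchanged |
| One responder excluded | 8/28 = 28.6% | below 9, does not reject |

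**4. Exclusions unrelated to response, not replaced.** Assumptions: losses occur in stage 2, stage 1 stays at 13, and the cut-off stays at 9. The formula in step 1 is used with X2 ~ Bin(n − 13, p).

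| Excluded | n | Type I error at 20% | Power at 38% |
|---|---|---|---|
| 0 | 29 | 0.100 | 80.4% |
| 1 | 28 | 0.084 | 77.4% |
| 2 | 27 | 0.070 | 73.7% |

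**5. Exclusions all non-responders, replaced to 29 evaluable.** Assumptions: a share e of treated patients is excluded, none of them responds, and recruitment continues until the evaluable numbers are 13 and 29. With a true all-treated ORR of 20%, the rate among evaluable patients is 0.20/(1 − e), which goes into the formula in step 1.

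| e | Evaluable rate | P(reject) |
|---|---|---|
| 5% | 0.20/0.95 = 0.211 | 0.128 |
| 10% | 0.20/0.90 = 0.222 | 0.164 |
| 15% | 0.20/0.85 = 0.235 | 0.210 |

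If excluded non-responders are not replaced, the number of responses is the same as without exclusion. The test result then does not change and only the reported rate rises.

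**The case against.** **Held days may count.** Pembrolizumab is given once every three weeks, so days on both drugs cannot mean dosing days for that drug. The phrase might mean time in the treatment period. The parenthesis about having received treatment points the other way, but 17.2 does not settle it. This stands as a limit on the hold route. It does not affect early death, progression or discontinuation.

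**The remedy may be partly there.** The 42-day rule is stated only for the primary endpoint, and ORR by iRECIST is a secondary endpoint whose CR and PR definitions match RECIST v1.1 (13.2.1). But 17.2 names no analysis set for it, and iRECIST is not the primary criterion. The gap remains.

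**The frequency is unknown.** This is true: the documents do not say how many patients would miss 42 days, so every size above is conditional.

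**A tempting stronger reading: the grade 2 dosing texts conflict and so decide who is analysed.** Section 9.3 recommends reduction for "grade 2 events that, if persistent, could become serious and/or intolerable", whereas Table 9.5.1.1 lists "No modification (may be held for significantly symptomatic grade 2 toxicity" and no reduction. A reader might infer that the denominator turns on which text is followed. The documents do not support that. Section 9.5 applies "in addition to management recommendations for cabozantinib-specific toxicities discussed in Section 9.3", Section 9.3 itself allows both delays and reductions, and "management may differ from this guidance based on the clinical judgement of the investigator". The triggers also differ: what an event could become if it persisted, against how symptomatic it is now. The documents give no frequency for grade 2 holds of 21 days or more. Other routes are at least as open, including the holds for grade 3 events; grade 3-4 events occurred in 68% of cabozantinib patients in CELESTIAL, at a 60 mg start.

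**A second stronger reading: the true type I error exceeds 0.10.** That needs excluded patients to be replaced and to be non-responders. Section 17.1 does not provide for replacing treated patients. Without replacement, exclusions unrelated to response lower the error.

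**Conclusion.** The point holds as one about Section 17.2. The primary ORR set depends on post-treatment events, and no RECIST v1.1 ORR in all treated patients is planned beside it.

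The design arithmetic itself is sound. The size is modest for one or two exclusions: about 2 percentage points on the reported ORR if both are non-responders, or 3 to 7 points of power if they are unrelated to response and not replaced. Close to the cut-off, a single excluded responder changes the conclusion. The rejection probabilities of 0.128 to 0.210 apply only under full replacement of excluded non-responders and should be read as illustrations.

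The hold route rests on held days not counting. The other routes need no such assumption.

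**What to change.** Add to 17.2:

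> *ORR by RECIST v1.1 with its confidence interval will also be reported in all patients who received any study treatment, counting those without a documented response as non-responders, beside the 42-day set.*

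Leave the primary set, the two-stage rule and the cut-off of 9 as they are. The dosing guidance in 9.3 and Table 9.5.1.1 needs no change on this account.

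This is a cheap improvement: one further analysis of data already collected, in the set that 17.2 already uses for safety. The downside is that the all-treated ORR may come out lower than the primary figure.

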9.3.1 Gastrointestinal disorders

GI perforation, GI fistula, and intra-abdominal and pelvic abscess: After starting treatment with cabozantinib, subjects should be monitored for early signs of GI perforation such as abdominal pain, nausea, emesis, constipation, and fever especially if known risk factors for developing GI perforation or fistula are present. Discontinue cabozantinib and initiate appropriate management in subjects who have been diagnosed with GI perforation or fistula.

Diarrhea: Subjects should be instructed to notify their physician immediately at the first signs of poorly formed or loose stool, or an increased frequency of bowel movements. **Please see Section 9.5.2 for evaluation and management of diarrhea and specific dosing instructions for both cabozantinib and pembrolizumab.**

Nausea and vomiting: Antiemetic agents are recommended as clinically appropriate for treatment or prophylaxis of nausea and vomiting, along with supportive care. Patients should be monitored for dehydration and electrolyte abnormalities, and correction of fluid and electrolyte disturbances should be implemented. Antiemetic medications should be assessed for potential drug interactions (see Section 8.0).

9.3.2 Non-gastrointestinal fistula

Complications from radiation therapy especially of the thoracic cavity including mediastinum have been identified as a possible predisposing risk factor for non-GI fistula formation in subjects undergoing treatment with VEGF pathway inhibitors. Discontinue cabozantinib and initiate appropriate management in subjects who have been diagnosed with a non-GI fistula.

9.3.3 Hemorrhage

Hemorrhagic events, including serious and sometimes fatal events, have been reported with cabozantinib. Subjects should be monitored for bleeding with clinical and laboratory assessments while on study. The risk of hemorrhage in cabozantinib-treated subjects with brain metastases has not been thoroughly analyzed. Subjects enrolled with treated and stable brain metastases should be monitored with a high index of suspicion if symptoms that could be due to a CNS hemorrhage occur.

Cabozantinib should be discontinued in subjects with serious and life-threatening bleeding events or recent hemoptysis (≥ 2.5 mL of red blood). For other clinically significant bleeding events, cabozantinib may be held and resumed after the bleeding resolves.

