9.3.11 Hepatocellular toxicity

Elevation of aminotransferases (ALT and AST): Evaluation of subjects with elevated transaminases or bilirubin should be individualized and guided by the presence of specific risk factors such as liver

conditions (e.g. liver cirrhosis, liver metastases, thrombosis of portal or hepatic vein), concomitant hepatotoxic medication, alcohol consumption, and cancer-related causes. Specifically, pembrolizumab is a potential cause of immune-mediated hepatitis and reactivation or flare of HBV or HCV in affected patients is a possibility. **Please see Section 9.5.3 for evaluation and management of liver toxicity and specific dosing instructions for both cabozantinib and pembrolizumab.**

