Hepatic encephalopathy not reversible and manageable by therapy ²	
 Discontinue drug.² 	
 Discontinue drug.²
Child-Pugh score > 8 points ²	
 Discontinue drug.² 	
 Hold drug until Child-Pugh score < 8, then resume at drug.²
GI bleeding suggestive or portal hypertension (e.g. esophageal or gastric varices)	
 Discontinue drug. 	
 Hold drug until bleeding has resolved and intervention completed if indicated (e.g. variceal banding) and patient is stable, then restart at the same dose as long as Child-Pugh score < 8 and ALT/AST/bilirubin elevations are < grade 3.

¹Once dose reduced, cabozantinib dose cannot be increased. Cabozantinib may be held up to 28 days, and pembrolizumab may be held up to 12 weeks.

²Some TKIs may cause hepatic encephalopathy, which is reversible and manageable. Patients with transient deterioration to Child Pugh score > 8 due to an ongoing reversible process such as treatable infection or dehydration can be reassessed for up to 2 weeks; if liver function improves to Child Pugh 5-7, consider reintroduction of pembrolizumab monotherapy and subsequent reintroduction of cabozantinib 1-2 weeks later if Child Pugh is 5-6 after discussion with study PI.

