16.3 Parameters of assessment for AEs and SAEs

AEs and SAEs must be assessed by the treating investigator and recorded based on the following parameters.

Parameter	Description	
CTCAE v5 grade	Grade 1	Mild; asymptomatic or mild symptoms; clinical or diagnostic observations only; intervention not indicated.
	Grade 2	Moderate; minimal, local or non-invasive intervention indicated; limiting age-appropriate instrumental ADL.
	Grade 3	Severe or medically significant but not immediately life-threatening; hospitalization or prolongation of hospitalization indicated; disabling; limiting self-care ADL.
	Grade 4	Life threatening consequences; urgent intervention indicated.
	Grade 5	Death related to AE
Seriousness	Does AE meet the definition of an SAE? (see Section 16.1 for definition)	
Duration	Record the start and stop dates of the adverse event or ongoing. If less than 1 day, indicate the length of time.	
Action taken	Did the AE cause each of the study drugs to be: held, dose reduced, discontinued, no action taken?	
Relationship to study drug(s)	What is the relationship of the AE to each of the study drug: unrelated, unlikely related, possibly related, probably related, definitely related? (see Section 16.2)	
Treatment required	Was treatment required for the AE (e.g. antibiotic, supportive medication)?	
Outcome	Is AE: ongoing, improved, stable, worsened, resolved?	

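### For lesser portal-hypertensive GI bleeds, Section 9.3.3 allows cabozantinib to be resumed while Table 9.5.3.1 says to stop it, and no text says which governs

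*Combined protocol and SAP*

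**What the plan says.** Three places deal with cabozantinib after a bleed.

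- **Section 9.3, general list:** "cabozantinib should be discontinued for the following AEs: visceral perforation or fistula formation, severe hemorrhage". Variceal bleeding is not named.
- **Section 9.3.3, Hemorrhage:** the drug is stopped for bleeds that are serious and life-threatening, or for recent hemoptysis. Then: "For other clinically significant bleeding events, cabozantinib may be held and resumed after the bleeding resolves".
- **Section 9.5.3, Table 9.5.3.1:** the row for "GI bleeding suggestive or portal hypertension (e.g. esophageal or gastric varices" discontinues cabozantinib and states no grade. For pembrolizumab the same row says "Hold drug until bleeding has resolved and intervention completed if indicated (e.g. variceal banding) and patient is stable", after which it is restarted if liver function allows.

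On how the sections relate, the opening of Section 9.5 says: "The sections below provide guidance on dose modifications for TRAEs, in addition to management recommendations for cabozantinib-specific toxicities discussed in Section 9.3". Section 9.2 names 9.3 and 9.5 side by side and adds that "management may differ from this guidance based on the clinical judgement of the investigator".

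**The concern.** A permission to resume and an instruction to stop can apply to the same patient. Someone managing a bleed would naturally open the subsection called Hemorrhage. There they find that cabozantinib may be restarted, with nothing to send them to a stricter row filed under liver toxicity. At stake is patient safety: an anti-angiogenic drug could be restarted after a variceal bleed against the protocol's own stricter rule. Different investigators could also treat the same event differently while each followed a text of the protocol.

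**Working it through.** No arithmetic applies; the check is a comparison of texts.

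**Step 1. Does the table row cover bleeds that are not life-threatening?** Yes. It sets no severity threshold, and its pembrolizumab cell expects the bleed to resolve, any banding to be done and the patient to be stable. Hold-and-restart is offered for pembrolizumab and withheld for cabozantinib within one row, so the stop looks deliberate. The encephalopathy and Child-Pugh rows above it carry a footnote that can let cabozantinib back in after a reversible deterioration. The bleeding row does not carry that footnote.

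**Step 2. Where do the texts differ?** Section 16.3 describes grade 3 as "Severe or medically significant but not immediately life-threatening; hospitalization or prolongation of hospitalization indicated". Section 16.1 makes an event serious if it requires inpatient admission, and also if it is life-threatening. Applied to a clinically significant portal-hypertensive GI bleed:

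| Grade | Section 9.3 list | Section 9.3.3 | Table 9.5.3.1 |
|---|---|---|---|
| 2 | stop not required | hold, may resume | discontinue |
| 3 | discontinue, taking severe as grade 3 | hold, may resume, if the bleed must be both serious and life-threatening; discontinue an admitted patient if either suffices | discontinue |
| 4 | discontinue | discontinue | discontinue |

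The conflict between 9.3.3 and the table is therefore at grade 2, plus grade 3 on the stricter reading of 9.3.3. If either condition suffices, the grade 2 conflict is confined to bleeds that meet no seriousness criterion. At grade 3 the general list in 9.3 already sides with the table.

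**Step 3. Does any text settle it?** No. Section 9.5 is additional to 9.3 and is not said to override it. Section 9.2 gives the two equal standing. The discretion clauses allow departure from the guidance but do not say what the default is. The treatment-discontinuation list in Section 12.0 does not mention bleeding.

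**Step 4. Is there a pointer?** Sections 9.3.1 (diarrhea), 9.3.7 (skin), 9.3.11 (liver), 9.3.13 (hematologic) and 9.3.19 (endocrine) each refer to their 9.5 counterpart. Section 9.3.3 does not. The pointer from 9.3 to the relevant table is in 9.3.11, "Please see Section 9.5.3 for evaluation and management of liver toxicity and specific dosing instructions for both cabozantinib and pembrolizumab", which concerns transaminases and bilirubin.

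**The case against.** The strongest reply is that the two rules can be obeyed together. Section 9.3.3 only says the drug may be resumed, while the table directs that it be stopped; the guidance is cumulative, and the row is the more specific text. An investigator who discontinues breaches neither. This stands as a reason why the effect is small. It does not remove the inconsistency: that the specific row prevails is an inference the protocol never states, and it can be argued the other way, since 9.3.3 is the section devoted to hemorrhage.

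A second reply is that the zone is narrower still. Because a life-threatening event is already serious under Section 16.1, requiring both conditions makes the word serious redundant, which favors reading either as sufficient. Grade 2 in Section 16.3 means minimal, local or non-invasive care, which fits a bleed needing banding poorly. Both points are fair, and they leave a small set of bleeds.

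Third, there are safeguards. Variceal bleeding in the past 6 months is excluded, varices are screened for and treated before study treatment, and dose modifications are reviewed at least monthly. These make the event less likely or catch it later; they do not say which rule applies. The table also concerns toxicity due to cabozantinib, so a bleed judged unrelated to either drug falls under Section 9.6.

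A reader might go further and infer that the protocol allows cabozantinib to be restarted after any variceal bleed. It does not: Section 9.3 stops it for severe hemorrhage, and 9.3.3 stops it for serious and life-threatening bleeds. Nor does the fatal upper GI hemorrhage reported in Section 1.4.1.5 show harm from this gap, because at life-threatening severity all three texts stop the drug.

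**Conclusion.** The inconsistency is real and narrow. For portal-hypertensive GI bleeding that is clinically significant but not serious and life-threatening, 9.3.3 permits resumption, Table 9.5.3.1 requires discontinuation, and no text ranks them. The grade 2 part holds on either reading of 9.3.3, subject to the seriousness limit in the comparison above. The grade 3 part rests on reading 9.3.3 as requiring both conditions, and Section 9.3 already points to stopping there.

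This is a small patient-safety correction, worth considering at the next revision. The documents give no rate for such bleeds, so no number of affected patients can be stated. There is no effect on the primary endpoint, type I error or power. A reader might infer an effect on who is evaluable under the exposure rule in Section 17.2, but the documents do not support one: permanent discontinuation cuts concurrent exposure at least as much as hold-and-resume, so the point does not favor either rule.

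**What to change.** Extend the last sentence of Section 9.3.3 ("For other clinically significant bleeding events, cabozantinib may be held and resumed after the bleeding resolves") with this clause:

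> …, except GI bleeding suggestive of portal hypertension (e.g. esophageal or gastric varices), for which cabozantinib is discontinued (Table 9.5.3.1).

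This keeps the rule the table appears to intend and supplies the missing pointer. The cost is one clause, with the usual amendment review under Section 20.0. Procedures, sample size and analysis do not change. The difference in wording between 9.3 (severe) and 9.3.3 (serious and life-threatening) would remain for other kinds of bleed; this clause does not address it.
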